## I. Research Objectives and Purpose

- Research Key Questions(s):** Can hypotension prediction index (HPI, ClearSight, Edwards Lifesciences, Irvine, USA) reduce time-to-treatment of epidural labor analgesia (ELA)-associated hypotension?
- Hypotheses:** HPI will have clinically significant reductions in time-to-treatment of ELA-associated hypotension compared to conventional non-invasive blood pressure monitoring methods.

## II. Research Significance

### 1. Background:

Despite decades of safe use, hypotension after epidural labor analgesia (ELA) remains the most common complication, experienced by an average of 1 of every 5 patients receiving ELA. Hypotension has safety ramifications to both mother and fetus and results in, at its mildest, maternal lightheadedness and nausea, and at its most severe, fetal acidemia and difficulties with fetal-to-neonatal transition. These safety concerns make *early detection, prevention, and treatment* of ELA-associated hypotension a *critical component* of safety on labor & delivery units worldwide.

Currently, conventional monitoring involves intermittent non-invasive blood pressure checks to detect and treat hypotension. The current American Society of Anesthesiologists Guidelines on Obstetric Anesthesia Practice recommend monitoring for hypotension, with most practices using non-invasive cuff measures, typically expected every 5-15 minutes. However, intermittent monitoring *potentially results in delays* in recognition and treatment of low blood pressure. Delays in treating epidural anesthesia-associated hypotension can result in inadequate maternal-fetal perfusion. Further, causes of hypotension after neuraxial in obstetric patients are primarily driven by reductions in systemic vascular resistance (SVR). Early detection of ELA-associated hypotension *is critically needed* to facilitate earlier treatments with vasopressors, typically consisting of either ephedrine or phenylephrine.

Our proposed solution involves using the hypotension prediction index (HPI, ClearSight, Edwards Lifesciences, Irvine, USA) to reduce time-to-treatment of epidural labor analgesia (ELA)-associated hypotension. The HPI algorithm on ClearSight uses arterial waveform features to predict hypotension, defined by mean arterial pressure (MAP) < 65 mmHg for at least 1 minute. The index ranges 0 to 100 with higher numbers reflecting a higher likelihood of subsequent hypotension. HPI has 92% sensitivity and specificity for predicting hypotension 5 min in advance, sensitivity 89% and specificity 90% for 10 min in advance and 88% and 87% for 15 min in advance. The sensitivity and specificity of HPI to accurately predict hypotension has also been validated with conventional invasive and non-invasive arterial waveforms, in both pregnant and non-pregnant cohorts. Other studies have similarly demonstrated the effectiveness of HPI in predicting hypotension in perioperative settings. The algorithm is approved for sale in Europe and the United States. To our knowledge, no study to date has rigorously assessed the utility of HPI in ELA compared to conventional monitoring, for the benefits of reduced time-to-treatment of ELA-associated hypotension.

This trial will investigate the ease of use and feasibility of the ClearSight monitoring system in comparison to the Conventional blood pressure monitor (upper arm cuff) during and after epidural-labor analgesia

placement. The pilot study will compare time-to-treatment of hypotension between conventionally monitored patients (Group CM) and those receiving HPI (Group HPI) monitoring by ClearSight, in a population of healthy people receiving ELA, and with the intent to expand this pilot study to a larger population of women to meet the power required to identify difference in time to treatment for hypotensive events.

## 2. **Significance/Rationale:**

This research question is significant because identifying patients at risk for ELA-associated hypotension will reduce the risk for the most common complication of ELA, hypotension. Earlier treatment of hypotension will improve safety and patient experience, by reducing maternal side effects (nausea, vomiting, lightheadedness) and fetal-neonatal risks (acid-base disturbances, neonatal transition challenges). It has the potential to change practice by facilitating clinical team performance to make earlier recognition, prophylaxis, and treatment decisions for the hundreds of thousands of patients receiving ELA annually.

## III. Investigational Plan

### 1. **Study design:** Prospective randomized controlled trial

### 2. **Methods:**

a. **Size of study groups(s):** The primary outcomes are 1.) ease and feasibility of use of the ClearSight monitoring system during labor and delivery, post-epidural-labor analgesia placement; and 2.) time-to-treatment of hypotension, defined as MAP <65 mmHg for more than 1 minute. Our initial pilot sample is expected to identify the ability to use the ClearSight monitoring in the labor and delivery suite, the patient adherence to the finger cuff monitors, and the feasibility of hypotension detection at the central monitors. The pilot sample (N = 30) is not expected to demonstrate significant differences in the relation between mode of blood pressure measurement and time-to-treatment of hypotension but should yield an estimate of the potential differences for a continuance of study.

b. **Environment and Estimated timeline to sample size acquisition:** UPMC Magee performs about 7,400 ELA annually, a range of 20-30 ELA daily. Based on a meta-analysis of trials, the estimated incidence of hypotension after initiation of neuraxial analgesia during labor is approximately 19% (range: 3-35%). Our internal data that shows approximately 20-30% of patients receiving ELA require treatment with a vasopressor within the first 4 hours of ELA initiation; we will use the conservative estimate of 20%. Our internal experience with similar trials also informs our timeline: in our prior experiences with similar labor and delivery trials we have achieved a consistent approach-to-recruit ratio of about 25%. Based on our volume, ELA utilization, eligibility criteria, and rates of ELA-associated hypotension, we estimate a total of 5-8 weeks of recruitment. A total of N=30 patients will be enrolled with a predicted 20% (n=6) experiencing hypotension events of interest.

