### c. **Outcomes:**

Primary outcome:

Ease of use of ClearSight blood pressure monitoring system

(0 – 10) Ratings from patient and patients' assigned nurse during ELA

Feasibility of blood pressure monitoring (yes/no response from assigned nurse regarding patient care.

Time-to-treatment of hypotension (minutes)

Secondary outcomes: (only exploratory)

Total time in hypotension with MAP <65 mmHg

Nausea

Vomiting

Total phenylephrine, mg

Total ephedrine, mg

Total intravenous fluids, mL  
Changes in fetal heart rate category  
Presence or absence of fetal heart rate decelerations within 1 hour of initiation of ELA  
CO, CI, SV, SVV

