Single-variable proportional hazards regression models will be created for each potential covariate of interest. Time-to-event estimates  $+$ /SE for both groups will be calculated from the single-variable models. Using  $P < 0.10$  from the univariate models as a threshold for inclusion in the multivariable model, the best-fit multivariable model will then be generated by removing variables with  $P > 0.05$  from the multivariable model in a backward stepwise fashion. To assess the primary outcome regarding relationship between treatment groups and “survival” (treatment-free) time, a proportional hazards model will be used to assess the effect of the monitoring type, with effects of covariates controlled in the best-fit multivariable model.

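### Usability and time-to-treatment are both primary and unranked; the sample is justified by usability, but the only headed primary analysis is of time-to-treatment

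*Combined protocol and SAP*

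**What the plan says.** All references are to the combined protocol and SAP.

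- **Primary outcomes.** Section III.2.a (size of study groups) opens with "The primary outcomes are 1.) ease and feasibility of use of the ClearSight monitoring system during labor and delivery" and continues with "2.) time-to-treatment of hypotension, defined as MAP <65 mmHg for more than 1 minute". Section III.2.c (Outcomes) lists under its primary heading an ease-of-use score, "Ratings from patient and patients' assigned nurse during ELA", on a 0 to 10 scale; then "Feasibility of blood pressure monitoring (yes/no response from assigned nurse regarding patient care"; then time-to-treatment in minutes. Only the secondary outcomes are labelled exploratory.
- **Hypothesis.** Section I concerns time-to-treatment alone: "HPI will have clinically significant reductions in time-to-treatment of ELA-associated hypotension compared to conventional non-invasive blood pressure monitoring methods".
- **Sample size.** Section III.2.a says the pilot sample should show whether ClearSight can be used on the unit, whether patients keep the finger cuff on, and whether hypotension can be detected at the central monitors. For time-to-treatment, the sample of 30 "is not expected to demonstrate significant differences in the relation between mode of blood pressure measurement and time-to-treatment of hypotension" but should give an estimate to inform a continued study.
- **Analysis.** Section III.4.b has one headed primary analysis, a survival analysis, and writes of the primary outcome in the singular: "To assess the primary outcome regarding relationship between treatment groups and “survival” (treatment-free) time, a proportional hazards model will be used". Its general paragraph has variables compared between groups by t test, rank test, chi-square or Fisher test, with P < 0.05 as the criterion. It does not name the ratings or the yes/no item.
- **Who wears the device.** Under section III.2.e all participants wear both ClearSight and the arm cuff, and Group CM is blinded to the ClearSight output.

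**The concern.** The parts of the plan point in different directions. The rationale for 30 patients points to usability. The hypothesis and the only headed primary analysis point to time-to-treatment. The two answer different questions, and a device can prove easy to use without shortening the delay to treatment, or the reverse.

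Two things are at stake. First, nothing fixed in advance says which result is the trial's primary finding, so any of several could be presented as such once the data are seen. Second, the measures that the sample is meant to establish would be analysed, if the general paragraph is followed, by a test that does not address their question. Similar ratings in the two arms are compatible with a device that is uniformly easy or uniformly hard to use.

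**Working it through.** **1. The plan's own figure.** Section III.2.b gives N = 30 and a 20% event rate. 30 × 0.20 = 6 patients with events, as stated.

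**2. What 6 events can show.** The plan gives no effect size, so the hazard ratios here are assumptions. With 1:1 allocation and two-sided 0.05, Schoenfeld's approximation is power = Φ(ln HR × √(d/4) − 1.96), with d = 6 and √(6/4) = 1.225.

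- HR 2: Φ(0.693 × 1.225 − 1.96) = Φ(−1.11) = 0.13
- HR 3: Φ(1.099 × 1.225 − 1.96) = Φ(−0.61) = 0.27

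This agrees with the plan's own statement that significance is not expected.

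**3. How many primaries.** Section III.2.a numbers two. Section III.2.c lists three items, or four measures if the patient and nurse ratings are analysed separately: patient rating, nurse rating, nurse yes/no, time-to-treatment.

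**4. Chance of at least one false positive if each is tested at 0.05.** For k independent tests this is 1 − 0.95^k: 0.0975 for two, 0.143 for three, 0.185 for four. With equally correlated normal test statistics (1,000,000 simulated replicates, critical value 1.96; the correlations are assumed):

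| Tests | r = 0 | r = 0.3 | r = 0.5 | r = 0.8 |
|---|---|---|---|---|
| 2 | 0.098 | 0.095 | 0.090 | 0.078 |
| 3 | 0.143 | 0.136 | 0.126 | 0.098 |
| 4 | 0.186 | 0.174 | 0.156 | 0.114 |

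The table gives every test its full 5% size. Fisher's exact test falls well short of that: with 15 per arm and a common yes-rate between 50% and 95%, its true size is about 0.05% to 1.7%. The four-test row is therefore an upper figure.

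**5. Does the default test answer the usability question?** Both arms wear ClearSight. A between-arm difference in ratings reflects how the output was used, not whether the device can be worn and worked with. The usability question is answered by the level of the rating or the proportion of yes responses.

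**6. Precision of a usability estimate.** The counts are illustrative. The exact 95% limits are the 0.025 quantile of Beta(x, n − x + 1) and the 0.975 quantile of Beta(x + 1, n − x).

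- 27 of 30 (90%): 73% to 98%
- 13 of 15 (87%): 60% to 98%

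The denominator matters. Group CM does not see the ClearSight output, so the nurse's feasibility item may be assessable only in Group HPI.

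**The case against.** The strongest reply is that this is an estimation pilot whose outcomes already have roles. Section II.1 (Background) states the intent to expand to a powered study, and section III.2.a assigns usability to the pilot and asks of time-to-treatment only an estimate. That is fair, and it makes the remaining problem mainly one of labels and analysis. It does not remove it: section III.4.b still places a multivariable hazards model under the primary heading and gives the usability primaries nothing of their own.

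A second reply is that no passage specifies a between-arm test of the ratings or the yes/no item, and that the Background's comparison with the arm cuff could be within-patient, since everyone wears both. This also stands in part. The default reading follows from a general paragraph that does not name these items, so the error rates are conditional on testing each one.

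Three stronger readings are tempting, and the documents do not support them.

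- A reader might infer that the plan expects treatment times not to differ. It says only that a significant difference is not expected at this size, and it still hypothesises a reduction.
- A reader might infer a tripled false-positive rate. That needs four separate full-size tests; two numbered primaries give less than double.
- A reader might infer that choosing one primary would settle whether the study continues. It would not, because that needs a progression criterion, and the plan gives none.

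**Conclusion.** The concern holds as a conflict between the sample rationale on one side and the hypothesis and headed analysis on the other, together with a default analysis that does not fit the usability measures. The unranked primaries carry a chance of at least one false positive of about 0.08 to 0.10 for two full-size tests and at most 0.11 to 0.19 for four, against a nominal 0.05. Those figures rest on assumed correlations of 0 to 0.8 and on each primary being tested at 0.05; the true values would be lower where Fisher's test is used. None of the plan's stated figures is wrong. This is a cheap improvement to what the pilot can claim.

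**What to change.** Make these edits in sections III.2.a, III.2.c and III.4.b:

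1. Name ease of use and feasibility of ClearSight as the pilot's primary objective. Report each measure as an estimate with a 95% confidence interval (exact for the yes/no item), with no between-group significance test.
2. State whether the denominator is all 30 patients or Group HPI only.
3. Count patients in whom ClearSight could not be used as feasibility failures. Section III.2.d lists inability to use the device, for any reason, as an exclusion. Applied after enrolment, that would remove the failures from the denominator and bias feasibility upward.
4. Relabel time-to-treatment as the key exploratory efficacy outcome, reported as an estimate with a 95% confidence interval for planning the continued study. Move the survival analysis under that heading, and reserve the test of the section I hypothesis for that study.
5. Reconcile the Background sentence that describes ease of use and feasibility as a comparison with the conventional monitor.

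The cost is editing only, with no new patients or data. The pilot gives up a primary significance claim on time-to-treatment that section III.2.a already says it cannot support, and any formal between-arm test of usability.

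### About 6 predicted events cannot give a time-to-treatment difference precise enough to size the continued study, yet the plan offers the pilot's estimate for that continuation and states no other basis for sizing.

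*Combined protocol and SAP*

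**What the plan says.** Time-to-treatment of hypotension is one of the primary outcomes (III.2.a and III.2.c), beside ease of use and feasibility of the monitor. Section I states the hypothesis that "HPI will have clinically significant reductions in time-to-treatment of ELA-associated hypotension".

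On size, III.2.a concedes that "The pilot sample (N = 30) is not expected to demonstrate significant differences" in time-to-treatment, but goes on to say that the sample "should yield an estimate of the potential differences for a continuance of study". III.2.b gives the expected yield: "A total of N=30 patients will be enrolled with a predicted 20% (n=6) experiencing hypotension events of interest". The rate comes from internal data that "approximately 20-30% of patients receiving ELA require treatment with a vasopressor within the first 4 hours of ELA initiation", of which the lower end is used. III.2.b also cites a literature average of 19% with a range of 3 to 35%.

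The Background (II.1) describes the pilot as run "with the intent to expand this pilot study to a larger population of women to meet the power required" for the time-to-treatment comparison. In the Statistical Analysis Plan (III.4.b), "a proportional hazards model will be used to assess the effect of the monitoring type", with treatment-free time as the survival time.

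The documents state no assumed effect, smallest important difference, target precision, or rule for sizing the continued study.

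**The concern.** The concession in III.2.a is about significance. The second half of the same sentence makes a separate promise, that the pilot will deliver a between-group difference for use in the continuation. Under proportional hazards the precision of that difference depends on the number of events, not on the 30 patients, and the plan expects 6 events, about 3 per arm.

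The by-arm difference is the only effect estimate that the plan offers for the continuation. If it were used to set the sample size, a large chance estimate could produce an underpowered trial. A small or reversed one could lead to an oversized trial, or to dropping a useful monitor by chance.

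**Working it through.** **The plan's own figure.** 30 × 0.20 = 6, which reproduces. At the upper internal rate, 30 × 0.30 = 9. At the ends of the literature range, 30 × 0.03 = 0.9 and 30 × 0.35 = 10.5. N = 30 has no power or precision calculation behind it to reproduce.

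**Inputs.** Allocation 1:1 (III.2.e), so 15 per arm; 4 hours of monitoring (III.2.e); significance level 0.05 (III.4.b). Assumed here because the documents do not state them: two-sided testing of the hazard ratio (HR), 80% power for the next trial, and true HRs of 1.5, 2 and 3. An HR above 1 means faster treatment in Group HPI.

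**Precision.** SE(log HR) = 2/√D for D events; the 95% CI factor is exp(1.96 × SE).
- D = 6: SE = 0.816, factor 4.95. An observed HR of 2 would have a CI of 2/4.95 = 0.40 to 2 × 4.95 = 9.9.
- D = 9: SE = 0.667, factor 3.69.
- D = 12: SE = 0.577, factor 3.10.
- In minutes, with 3 v 3 treated patients: t(0.975, 4 df) × √(2/3) = 2.27 SD half-width.
- Chance that an arm has no events, at 20% in both arms: 1 − (1 − 0.8^15)² = 6.9%. The HR is then not estimable.

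**Consequence if the next trial were sized from the pilot HR.** Events needed = 4(1.96 + 0.84)²/(ln HR)². Pilot estimates were drawn from a normal distribution with mean ln HR and variance 4/D, and each was put into that formula.

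| True HR (assumed) | 1.5 | 2 | 3 |
|---|---|---|---|
| Events truly needed | 191 | 66 | 27 |
| 6 events: wrong direction | 31% | 20% | 9% |
| 6 events: target at most half the need | 42% | 36% | 29% |
| 6 events: right direction, within a factor of 2 | 14% | 24% | 37% |
| 6 events: target at least double the need | 13% | 20% | 26% |
| 9 events: right direction, within a factor of 2 | 17% | 29% | 44% |
| 12 events: right direction, within a factor of 2 | 20% | 33% | 50% |
| 6 events: median real power, favourable pilots | 34% | 58% | 73% |

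Columns may miss 100% by rounding. The within-a-factor-of-2 row for 6 events can be checked in closed form as Φ((√2 − 1)·ln HR/SE) − Φ((1/√2 − 1)·ln HR/SE), which gives 13.9%, 23.6% and 36.5%.

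The median power for HR 2 can be followed by hand. 80.2% of pilots are favourable, and the median favourable log HR is 0.693 + 0.816 × 0.251 = 0.898. The derived target is 31.4/0.898² = 38.9 events. The real power is Φ(√38.9 × 0.693/2 − 1.96) = Φ(0.20) = 58%.

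**Check without the normal approximation.** Cox models were fitted to simulated trials (15 per arm, exponential times, censoring at 240 min, 20% control rate). With no true difference, the middle 95% of estimable HRs ran from 0.21 to 4.66. The target was within a factor of 2 in 15% (HR 1.5) and 25% (HR 2) of pilots.

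**Pooled proportion.** 6/30 has an exact 95% CI of 8 to 39%.

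**Type I error, conditional scenario only.** Suppose success could be claimed either at the pilot or at a final analysis that includes the pilot patients, each at 0.05. The overall error is 1 − P(|Z1| < 1.96, |Z2| < 1.96) with correlation √f, where f is the pilot's share of the information. This is 9.5% at f = 0.1 and 8.9% at f = 0.3.

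**The case against.** The strongest reply is that the plan promises only an estimate, not a usable one, and nowhere says that the next sample size will be computed from the pilot HR. It puts feasibility first and admits that significance is not expected. This stands in part: the sizing use is an inference from III.2.a and II.1 read together, and the harm follows only if the estimate is used that way. It does not remove the point, because the estimate is offered for the continuation without any qualification about its precision and without any other basis for sizing.

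Second, 6 may understate the events in the model. Group HPI is also treated on HPI alerts (Hypotension Treatment Protocol), and the usual systolic pressure and fetal heart rate triggers continue in both groups (Hypotensive Event Measurement). That is fair, and is why 9 and 12 events are shown. Even 12 events reach a factor of 2 in at most about half of pilots.

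Third, the effect sizes are assumed, and a large effect is kinder: at HR 3 with 9 events, the direction is wrong in 5% and median real power is 77%. That also stands, though 56% of those pilots still have the wrong direction or a target off by at least a factor of 2.

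A reader might also infer that expanding the pilot inflates the final type I error to about 9%. The documents do not support this. They do not say that pilot patients will be pooled, that a significant pilot counts as success, or that a by-arm P value triggers the expansion.

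**Conclusion.** The point holds as one of precision and wording. At 6 to 9 events the HR is known only to within a factor of about 5 to 3.7 either way. For true HRs of 1.5 to 3, a study sized from the estimate would have the wrong direction or a target off by at least a factor of 2 in 63 to 86% of pilots at 6 events, and in 56 to 83% at 9.

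The imprecision follows from the plan's own event count. The mis-sizing figures rest on assumed effect sizes, 80% power, and the inferred use of the pilot estimate. Mis-sizing is therefore a risk that the present wording leaves open, not a certain outcome. The feasibility and ease-of-use aims, which all 30 patients can inform, are not in question.

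**What to change.** Replace the sentence in III.2.a with a statement that:
- the by-arm time-to-treatment difference will be reported descriptively with its 95% CI, and will not by itself set or trigger the size of the continued study;
- the pilot supplies the feasibility figures, the pooled arm-blind proportion with hypotension events and its exact CI, and the spread of the times;
- the continued study will be sized on a pre-stated smallest worthwhile reduction in time-to-treatment.

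Only if pilot patients are to be kept in the expanded trial, add that the size decision is made on arm-blind data and that nothing is claimed from a by-arm test at the pilot.

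The cost is a change of protocol and SAP wording and a less ambitious stated aim for the pilot. No patients, visits or procedures change.
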